3.4 PATIENT-REPORTED OUTCOMES

The following questionnaires will be used to evaluate general and disease-specific quality of life, and device usability. Results will be assessed at 13 weeks compared to baseline (Intervention and Control group):

- Clarke Hypoglycemia Awareness
- EQ-5D-3L
- Type 1 Diabetes Distress Scale (T1-DDS)
- Diabetes Quality of Life-brief (DQOL-brief)
- DAWN Impact of Diabetes Profile (DIDP)
- Hypoglycemia Confidence Scale (HCS)
- Pittsburgh Sleep Quality Index (PSQI)
- System Usability Scale (SUS)
- Insulin Dosing Systems: Perceptions, Ideas, Reflections, and Expectations (INSPIRE)

3.5 PERIOD 2 OUTCOMES

The following outcomes will also be assessed at the end of Period 2 (France participants only):

- Ratio of participants joining Period 2 per group
- Maintenance of use
- Incidence rate of severe hypoglycemia
- Incidence rate of diabetic ketoacidosis (DKA)

The following outcomes will also be assessed at the end of Period 2 as compared to baseline values (2-week standard therapy period) (France participants only):

- HbA1c (at 3, 6, 9 and 12 months)
- Glycemic outcomes
 - Percentage of time <54 mg/dL
 - Percentage of time <70 mg/dL
 - Percentage of time >180 mg/dL
 - Percentage of time in range (70-180 mg/dL)
 - Percentage of patients having time in range ≥70%
 - Percentage of patients having time below range <4%
 - o Mean glucose
 - Change from baseline in HbA1c
 - Proportion of participants with HbA1c <7%

- Proportion of participants with HbA1c <8%
- Percentage of time spent in Automated mode
- Change from baseline in BMI (at 6 and 12 months)
- Insulin usage (units, units/kg)
- Patient-reported outcome questionnaires at 6 months and 12 months (or withdrawal from study):
 - DQOL-brief used to assess the relative burden of an intensive diabetes treatment regimen
 - HCS used to measure hypoglycemia awareness, hypoglycemia frequency, severity, and impact

4 ANALYSIS OF PRIMARY ENDPOINT

4.1 SAMPLE SIZE

The sample size estimation is based on the following assumptions:

- Power of 90% and two-sided significance level of 5%
- Difference between groups of 10% in TIR 70-180 mg/dL
- Standard deviation of 16.5% in each group
- 2:1 randomization (Intervention:Control)

Under these assumptions, a total sample size of 131 participants is required (87 Intervention, 44 Control). To allow for pre-randomization attrition of up to 15%, and post-randomization attrition of up to 22.9%, a total sample size of up to 200 will be enrolled to give 170 participants randomized and 131 participants completing the 13 weeks. The anticipated difference in TIR 70-180 mg/dL was projected from the OP5 pivotal study.

The sample size calculations were performed using PASS 2021.

Standard residual diagnostics will be performed for all analyses. It is expected that the primary outcome will follow an approximately normal distribution, however, residual values will be examined to confirm an approximate normal distribution. If values are highly skewed, then robust regression using M-estimation will be used instead. In this case, the model will include TIR 70-180 mg/dL during the 13 weeks randomized period as the dependent variable, baseline TIR 70-180 mg/dL as a covariate, and missing data will be handled using multiple imputation.

The primary analysis will utilize the mITT analysis set and will be tested at a two-sided significance level of 5%.

4.3 SENSITIVITY ANALYSIS

Missing data handling in described in Section 7.6 of this document. The following sensitivity analysis will be performed for the primary endpoint.

4.3.1 Complete Cases Only

The primary analysis will be replicated including only participants with non-missing TIR 70-180 mg/dL at baseline and follow-up. This assumes missing completely at random (MCAR).

4.3.2 Multiple Imputation Assuming MAR

Consider a model with TIR 70-180 mg/dL during the 13-week randomized period as the dependent variable, randomized treatment group, baseline TIR 70-180 mg/dL, age, sex, and duration of diagnosis as fixed effects and site as a random effect.

Missing data will be handled using multiple imputation assuming missing at random (MAR). The imputation model will include treatment group, baseline TIR 70-180 mg/dL, age, sex, and duration of diagnosis. Multiple imputation will involve the following steps:

- 1. Generate 100 imputed data sets.
- 2. Fit the mixed effects linear regression model on each imputed dataset. Calculate the point estimate and standard error of the treatment group difference for each imputed dataset.
- 3. Pool the estimates across imputations to get an overall point estimate and confidence interval for the treatment group difference.

4.3.3 Two-way Tipping Point Analysis

A two-way tipping point sensitivity analysis will be performed to evaluate the possibility of missing not at random (MNAR).

First, multiple imputation will be applied to missing TIR 70-180 mg/dL assuming MAR, as described above. This procedure will then be repeated applying various shifts to the imputed values. Since the reasons for missing data may vary by treatment group, a separate shift will be applied for each treatment group. A shift of zero for both treatment groups is equivalent to the model assuming MAR. A positive shift indicates that we expect TIR 70-180 mg/dL to be worse in that treatment group for those with missing values than those with observed data. The range of shifts that are considered will include scenarios where the outcomes for patients missing data are worse among patients randomized to the treatment arm than those randomized to the control arm. The goal is to examine how far one needs to shift for the results of the study to tip from significant to not significant for between-treatment comparison. Tipping points that change the significance will be reported and clinically evaluated for whether such points are considered plausible.

4.3.4 Covariate Adjustment

The primary analysis includes a pre-specified list of covariates. As an additional sensitivity analysis, any baseline demographic or clinical characteristics observed to be imbalanced between treatment groups will be added as covariates to the model for the primary endpoint. The determination of a meaningful baseline imbalance will be based on clinical judgement and not a p-value.

4.4 POOLABILITY

As the study plans to enroll site in the US and France, the poolability will be assessed first by country, and then by site.

A repeated measures mixed effect model with treatment group and country as fixed effects and TIR 70-180 mg/dL at baseline and during the week 13 randomized period as the dependent variable will be fit for the comparison of treatment groups. The model will also include treatment group by country interaction term. A p-value for the interaction term of <0.15 will be considered to indicate heterogeneity. If the p-value for the interaction term from the model is <0.15, a repeated measures mixed effect model with treatment as fixed effect and country as random effect will be fit.

Further, within each country, a similar model with treatment and study site as fixed effects; TIR 70-180 mg/dL at baseline and during the week 13 randomized period as the dependent variable; and a treatment by site interaction term will be fit. A p-value for the interaction term of <0.15 will be considered to indicate heterogeneity within that country. If the p-value for the interaction term from the model is <0.15, a repeated measures mixed effect model with treatment as fixed effect and study site as random effect will be fit.

For the poolability analysis that assesses homogeneity within each country, sites with ≤5 participants contributing to analysis will be combined into pseudo-centers of at least 10 participants, or combined with existing centers to make sure that each site contributes at least 10 participants. If site is included in other analyses, e.g., random effect in the analysis of primary endpoint, the same approach of combining sites will be used.

4.5 SUBGROUP AND STRATIFIED ANALYSES

Regardless of results of poolability analysis of primary endpoint, the primary endpoint and any secondary endpoints found statistically significant in the hierarchical testing will be further explored to understand the treatment effect. The general approach for these exploratory analyses will be to add an interaction term for the subgroup factor by treatment to the primary and secondary endpoint models described above. Additional factors may be identified based on study results or those deemed of interest based on clinical assessment.

The endpoint results for the factors for which the interaction term was statistically significant (at a two-sided 5% significant level) will be presented in a stratified manner. Categorical variables will be stratified by category (although multiple categories may be combined for ease of interpretation). Continuous variables will be stratified based on mean/median value or clinical or scientific justification. At a minimum, additional stratifications will include:

- Country (USA vs. France)
- Sex
- Race/Ethnicity (White non-Hispanic vs. Other)
- Age
- BMI (≤25 vs >25 kg/m²)
- Day and night (daytime: 6AM to <12AM; nighttime as 12AM to <6AM)
- Baseline value of the endpoint

5 ANALYSIS OF OTHER ENDPOINTS

5.1 ANALYSIS OF SECONDARY ENDPOINTS (PERIOD 1)

To preserve the family-wise type 1 error for selected key secondary endpoints, a fixed sequence hierarchical testing approach will be used. If the primary endpoint is found to be statistically significant at a two-sided significance level of 5%, testing for secondary endpoints can commence. Secondary endpoints will be tested in a hierarchical fashion at a one-sided significance level of 2.5% (or two-sided significance level of 5% as appropriate). Each endpoint with a two-sided p-value ≤ 0.05 (or one-sided p-value of ≤ 0.025 , as appropriate) is considered to be met until a secondary endpoint with a two-sided p-value ≥ 0.05 (or one-sided p-value of ≥ 0.025 , as appropriate) is encountered. This process continues iteratively moving to the next endpoint down on the list until a non-significant result is observed, or all endpoints have been tested. If a non-significant result is encountered, then formal statistical hypothesis testing is terminated and any variables below on the list are not formally tested.

Regardless of the results of the hierarchical testing, summary statistics appropriate to the distribution will be tabulated for each key secondary endpoint by treatment group. A 95% confidence interval for the treatment effect will also be calculated for all key secondary outcomes listed above. However, a confidence interval that is below zero (superiority) or that is below the non-inferiority margin (noninferiority) will not be considered a statistically significant result if an outcome variable higher on the hierarchical list failed to reach statistical significance.

The secondary endpoints will be analyzed using a repeated measures linear mixed effects model with the endpoint at baseline and at 13 weeks as the dependent variable. The correlation between baseline and follow-up will be modelled using an unstructured covariance matrix. The model will include randomized treatment group, age, sex, and duration of diagnosis as fixed effects and site as a random effect. This model adjusts for baseline value of the endpoint by forcing the treatment groups to have the same mean value at baseline. Missing data will be handled by using a direct likelihood approach which will allow participants to be included even if they only have data at one of the time points.

Binary PRO-derived endpoints will be presented as number and percent of participants achieving treatment success with corresponding 95% asymptotic confidence limits in each group. Binary endpoints will be analyzed using a logistic mixed effects model with the endpoints as the outcome. The following variables will also be included in the model as fixed effects: randomized treatment group, age, sex, duration of diagnosis, and baseline continuous value of the outcome being tested. In addition, the model will adjust for site as a random effect. A 95% confidence interval for the treatment group adjusted risk difference will be produced using parametric bootstrapping.

Standard residual diagnostics will be performed for all secondary analyses. Residual values will be examined to confirm an approximate normal distribution. If values are highly skewed, then robust regression using M-estimation will be used instead. In this case, the model will include the endpoint at 13 weeks as the dependent variable, baseline value of the endpoint as a covariate, and missing data will be handled using multiple imputation.

The secondary analyses will utilize the mITT analysis set, and will be tested at a two-sided significance level of 5% or a one-sided significance level of 2.5%, as appropriate. If there is evidence of heterogeneity either across countries or study sites based on the poolability analysis, a random effect for country or site, as appropriate, will also be included.

The secondary endpoints will be testing in the following order:

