11.2 Secondary Endpoints and Hypotheses

The following secondary per-participant endpoints will be evaluated and compared in the Intervention group vs. Control group at the end of the 13-week randomized period:

- Percentage of time <54 mg/dL (non-inferiority)
- Percentage of time >180 mg/dL
- Mean glucose
- Change from baseline in A1C
- Percentage of time < 70 mg/dL
- Change from baseline in Type 1-Diabetes Distress Scale (T1-DDS) total score at 13 weeks
- Change from baseline in Hypoglycemia Confidence Scale (HCS) total score at 13 weeks
- Change from baseline in Diabetes Quality of Life-brief (DQOL-brief) total score at 13 weeks

Secondary Endpoints will be tested in a hierarchical fashion.

The null and alternative hypotheses for the secondary endpoints are as follows:

Percentage of time < 54 mg/dL (non-inferiority):

$$H_0: \mu_I - \mu_C \geq 1\%$$

$$H_A: \mu_I - \mu_C < 1\%$$

Where μ_I and μ_C are the population means of percentage of time < 54 mg/dL during the 13 weeks in the Intervention and Control groups, respectively. The non-inferiority margin is 1%. If the upper bound of the two-sided 95% confidence interval for the difference (μ_I

minus μ_c) is $<1\%$, non-inferiority will be established. If the upper bound of the two-sided 95% confidence interval for the difference (μ_i minus μ_c) is $<0\%$, superiority of the Intervention group compared to the Control group will be established.

Percentage of time >180 mg/dL:

$$H_0: \mu_i - \mu_c = 0$$

$$H_A: \mu_i - \mu_c \neq 0$$

Where μ_i and μ_c are the population means of percentage of time >180 mg/dL during the 13 weeks in the Intervention and Control groups, respectively.

Mean glucose:

$$H_0: \mu_i - \mu_c = 0$$

$$H_A: \mu_i - \mu_c \neq 0$$

Where μ_i and μ_c are the population means of mean glucose during the 13 weeks in the Intervention and Control groups, respectively.

Change from baseline in A1C:

$$H_0: \mu_i - \mu_c = 0$$

$$H_A: \mu_i - \mu_c \neq 0$$

Where μ_i and μ_c are the population means of change from baseline in A1C after 13 weeks in the Intervention and Control groups, respectively.

Percentage of time < 70 mg/dL:

$$H_0: \mu_i - \mu_c = 0$$

$$H_A: \mu_i - \mu_c \neq 0$$

Where μ_i and μ_c are the population means of percentage of time < 70 mg/dL during the 13 weeks in the Intervention and Control groups, respectively.

Change from baseline in Type 1-Diabetes Distress Scale (T1-DDS) total score at 13 weeks:

$$H_0: \mu_i - \mu_c = 0$$

$$H_A: \mu_i - \mu_c \neq 0$$

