1 PURPOSE

The purpose of this Statistical Analysis Plan (SAP) is to describe the statistical methodology that is used to confirm the safety and effectiveness of the Omnipod 5 Automated Glucose Control System in patients with type 1 diabetes. Should there be a discrepancy between the OP5-003 study protocol(s) and this SAP, the content of the SAP shall prevail.

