5.1.1 Percentage of Time <54 mg/dL (Non-Inferiority)

The hypotheses associated with this endpoint are:

- o H₀: μ₁ μ_C ≥ 1
- ο H_A: μι μc < 1

where μ_l and μ_c are the population means of per-participant percentage of time <54 mg/dL as measured by the study CGM during the 13 weeks in the Intervention and Control groups, respectively

The non-inferiority margin will be set to 1%. The calculation of percentage of time in a specified range is described in Section 7.4. If the upper bound of the two-sided 95% confidence interval (corresponding to 1-sided 97.5% CI) for the difference (μ_I minus μ_C) is <1%, non-inferiority will be established. If the upper bound of the two-sided 95% confidence interval for the difference (μ_I minus μ_C) is <0%, superiority of the Intervention group compared to the Control group will be established.

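### The skewness switch in SAP 5.1 lets M-estimation decide the time <54 mg/dL non-inferiority test, although its 1% margin is defined on means

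*SAP*

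**What the plan says.** For time <54 mg/dL, SAP 5.1.1 defines the parameters under test as quantities that "are the population means of per-participant percentage of time <54 mg/dL as measured by the study CGM during the 13 weeks". It fixes the margin in percentage points ("The non-inferiority margin will be set to 1") and compares the upper limit of the two-sided 95% interval for the difference with that margin. The same interval is read for superiority against 0. Protocol 11.2 agrees: its parameters "are the population means of percentage of time < 54 mg/dL during the 13 weeks in the Intervention and Control groups".

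The default analysis in SAP 5.1 targets a mean difference: "The secondary endpoints will be analyzed using a repeated measures linear mixed effects model". The same section then applies residual diagnostics to every secondary analysis ("Residual values will be examined to confirm an approximate normal distribution") and adds: "If values are highly skewed, then robust regression using M-estimation will be used instead". The replacement model regresses the 13-week value on the baseline value and uses multiple imputation for missing data.

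Protocol 11.2 names only linear mixed models, but it cannot override the switch: "Should there be a discrepancy between the OP5-003 study protocol(s) and this SAP, the content of the SAP shall prevail". Protocol 12.7 gives the SAP the same precedence.

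**The concern.** The hypothesis concerns one parameter and the decisive interval may concern another. M-estimation down-weights large residuals. If extra hypoglycemia on the Intervention device falls mainly on participants who already have much of it, or on a susceptible minority, those are the values that lose weight. The estimate then understates the mean difference that the margin is meant to limit.

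This is the trial's only non-inferiority test against a hypoglycemia margin, and it comes first in the secondary hierarchy. A false pass here also opens every later secondary test. Because no cut-off is given, the choice of estimator is left to judgement after the values have been examined.

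**Working it through.** **1. The plan's own figures.** SAP 4.1 requires 131 completers (87 + 44) for the primary endpoint: 90% power, two-sided 5%, difference 10, SD 16.5, 2:1. A two-sample noncentral-t calculation gives power 0.902 at 87/44, so this reproduces. Attrition also reproduces: 131/(1 − 0.229) = 169.9, about 170 randomized, and 170/(1 − 0.15) = 200 enrolled. At 2:1, 170 splits into about 113 and 57. The documents give no power, mean, SD or shape for time <54 mg/dL.

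**2. The two estimators.** The mean-based model is Y = a + τT + bX + e, with Y the 13-week value, T treatment and X baseline. With complete data its τ equals the maximum-likelihood estimate from the planned baseline-constrained model (covariates and site aside), and it targets the mean difference. M-estimation solves Σ ψ(r/s)·x = 0, where ψ limits the influence of large scaled residuals. The two targets agree for a uniform shift but need not when the arms differ in shape.

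**3. Inputs.** From the documents: margin 1, upper two-sided 95% limit, nominal one-sided 2.5%, 113 against 57. Assumed, because the documents are silent:
- gamma participant levels, control mean m = 0.3, 0.5 or 0.8, shape 0.7 or 1.5 (six cells); gamma noise at baseline (shape 2) and follow-up (shape 8);
- the switch fires if residual skewness exceeds 1, 2 or 3;
- Huber weights (c = 1.345) or bisquare weights (c = 4.685).

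The true mean difference is always 1.0, delivered in different shapes. The proportional case multiplies by (m + 1)/m: 1.3/0.3 = 4.3, 1.5/0.5 = 3 and 1.8/0.8 = 2.25. A variable (gamma) or constant excess in a fraction f has mean 1/f, so 1/0.3 = 3.3 points each at 30%. There were 2,000 trials per cell, with Monte Carlo error of at most about 1.1 points.

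**4. Results.** Rate of declaring non-inferiority, whole procedure (Huber if the switch fires, otherwise the planned model), range over the six cells:

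| Shape of the excess | Cut-off 1 | Cut-off 2 | Cut-off 3 |
|---|---|---|---|
| Proportional to level | 55-92% | 27-64% | 9-28% |
| Variable, in 30% | 83-99% | 64-94% | 11-32% |
| Variable, in 50% | 29-67% | 8-31% | 2-3% |
| Variable, in all | 6-26% | 2-4% | 1-2% |
| Constant, in random 30% | 26-53% | 0-2% | 0-1% |
| Constant, in random 50% | 0-1% | 0-1% | 0-1% |
| Uniform shift | 2-3% | 2-3% | 2-3% |

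The mean-based model gave 0-4% in all these cases. The average Huber estimate, against a true 1.0, was 0.58-0.76 (proportional) and 0.26-0.47 (variable, 30%). With bisquare weights the proportional case gave 80-97% / 37-66% / 11-29% and the variable 30% case 99-100% / 73-95% / 11-32%.

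**5. How often the switch fires (cut-offs 1 / 2 / 3).** Proportional: 95-97% / 42-64% / 10-25%. Variable, 30%: 100% / 73-95% / 10-32%. No true difference: 95-97% / 34-57% / 6-18%. At cut-off 2, a variable excess in 30% thus makes the switch more likely than no excess does.

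**6. Check under another distribution.** Log-normal data with M-estimation always applied, 113/57, control means 0.3-1.0 and coefficients of variation 1.0-1.5, gave 55-98% (Huber) and 84-100% (bisquare) for a proportional excess. Milder skew (mean 1 with CV 0.5, or mean 2 with CV 0.7) gave 16-21% and 28-37%. A uniform shift gave about 3-4% with either. The mean-based model gave 1.4-6.6% across all the log-normal scenarios.

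**The case against.** The strongest reply is that SAP 5.1 is a general rule and SAP 5.1.1 a specific one. Since 5.1.1 names the difference in means, a statistician could keep the mean-based interval without breaching the plan. That reading is possible, but the switch covers all secondary analyses, says *instead* and exempts nothing. A plan that supports both readings leaves the decision open after the data are seen.

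Second, the rates depend on the assumed shape, affected fraction, cut-off and weight function, and run from about 1% to 99% across the variable-excess cases. This stands. An excess spread over all participants does little harm at cut-offs 2 and 3.

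Third, a true difference of 1.0 is large. At an assumed control mean of 0.5 (shape 0.7), both methods passed in 100% of trials at a true +0.25. At +0.5, a doubling, the mean-based model passed in 91-94% and the switch procedure in 91-100%. The choice therefore matters mainly beyond a doubling. The margin is nevertheless where the type I error of this test is defined.

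Fourth, the mean-based model is not exact either. It gave 7-10% under a log-normal level (SD 1.3) with proportional increase and about 8% with a variable excess in 5%. This stands, but the switch procedure gave 80-100% there at cut-offs 1 and 2.

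The gamma simulation assumes complete data and omits site, age, sex, diabetes duration and multiple imputation. None of these changes the cause, which is the mismatch of parameters. Protocol 12.5 also allows non-parametric methods for non-normal data, but in general terms; it neither restates this margin nor outranks the SAP.

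Arm-level summaries ("summary statistics appropriate to the distribution will be tabulated for each key secondary endpoint by treatment group") and the severe hypoglycemia analyses in SAP 5.2.5 could reveal a large tail excess. They do not decide this test.

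**Conclusion.** The concern holds. It is certain from the text that the margin and hypotheses are on means, that the switch covers this test without exemption, and that neither cut-off nor weight function is given. The consequence is conditional: the switch must fire, and the excess must be proportional to level or concentrated in an upper tail. If both occur, false non-inferiority at the margin can be many times the nominal 2.5%, though inflation shrinks as the cut-off rises. These sizes rest on assumed distributions, so confidence in them is medium.

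The superiority reading uses the same interval and shares the mismatch. SAP 2.4 ties study success to the primary endpoint alone, so that is not at stake. This should be fixed because a stated rule can produce a wrong non-inferiority conclusion.

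**What to change.** In SAP 5.1 and 5.1.1, exempt the time <54 mg/dL non-inferiority test, and the superiority reading of its interval, from the M-estimation switch. State that the planned mixed model's 95% interval for the mean difference is the sole basis for comparison with 1% and with 0%. Report M-estimation, and a bootstrap or heteroscedasticity-consistent interval for the mean difference, as supportive only, so that they neither overturn nor rescue the decision. Neither interval is clearly better calibrated: the HC3 version gave 1-6% in the gamma cases and 10-14% in the heavier tails, and the percentile bootstrap 1.5-9%.

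If the sponsor prefers M-estimation to decide, the SAP must define the quantity it targets, name the weight function and cut-off, and justify a margin on that scale. The first option is shorter and leaves hypotheses, margin and sample size unchanged.

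The cost is two or three sentences and a wider interval. With no true difference the half-width was 0.07-0.24 points against 0.04-0.13 for Huber, and both methods declared non-inferiority in 100% of simulated trials. With a variable excess in 30% it was 0.52-0.58 against 0.14-0.30, so a true excess below 1.0 that sits in a few participants could fail the test.
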